6.12.3. Deaths, Other Serious Adverse Events, and Other Notable Adverse Events

The general summary of adverse of events is described in the H0P-MC-CPMP SAP Version 5.

Treatment emergent adverse events of special interest will be reported separately by preferred term. These events include

- infusion site reactions (preferred MedDRA term)
- hypersensitivity and infusion-related reactions
 - Anaphylactic reaction (SMQ)
 - Anaphylactic/anaphylactoid shock conditions (SMQ)
 - Angioedema (SMQ)
 - Hypersensitivity (SMQ)
 - Infusion-related reaction (preferred MedDRA term)
- dermatological adverse events
 - Severe cutaneous adverse reactions (SMQ)
 - Drug reaction with eosinophilia and systemic symptoms syndrome (SMQ)
- abnormal renal function
 - Renal function analyses (MedDRA HLT)
 - Renal failure and impairment (MedDRA HLT)

CCI

CCI

CCI

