8.2. Adverse Events and Serious Adverse Events

8.2.1. Infusion Site Reactions

Symptoms of a local infusion site reaction may include erythema, induration, pain, pruritus, and edema. If an infusion site event is reported, the AE will be recorded, and additional data will be provided to the sponsor in the CRF.

Additional blood and urine samples should be collected as described in BP01 Section 10.3, Appendix 3, “Recommended Laboratory Testing for Hypersensitivity Events”. Laboratory results are provided to the sponsor via the central laboratory.

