6.17. Totality of Evidence for Safety

The totality of evidence for safety analysis has been briefly described in the H0P-MC-CPMP SAP Version 5. The key safety events to be considered for H0P-MC-BP01 are listed below by domain:

General Adverse Event Information

- Serious adverse events related to study treatment
- Study discontinuation due to adverse event
- Treatment discontinuation due to adverse event

Cardiovascular

- QTc prolongation: > 60 msec increase
- Serious cardiac disorders adverse event

Liver function

- Hy's Law case: Serum total bilirubin ≥ 2 and ALT ≥ 3 for at least one visit during the double-blind treatment period

Metabolic function

- Serious hypoglycemia adverse event
- Treatment emergent HbA1c: Shift from low/normal at baseline to high at least once during the double-blind treatment period

Renal function

- Treatment emergent abnormal eGFR: Shifts
 - Mild at baseline to moderate/severe during the double-blind treatment period
 - Moderate at baseline to severe during the double-blind treatment period

Dermatological

- Serious or severe dermal reactions

Hypersensitivity

- Moderate to severe infusion site reactions
- Serious or severe hypersensitivity reactions

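### The infusion-site-reaction AESI is searched at preferred-term level with no grouping, so on a literal reading its summary can leave out local reactions coded by sign

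*SAP*

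**What the plan says.** SAP 6.12.3 opens its AESI list with the rule that "Treatment emergent adverse events of special interest will be reported separately by preferred term". The entry for local reactions reads "infusion site reactions (preferred MedDRA term", with no terms listed.

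The remaining groups in the list are specified as follows:
- Hypersensitivity and infusion-related reactions: four SMQs, among them "Hypersensitivity (SMQ", plus one single term, "Infusion-related reaction (preferred MedDRA term".
- Dermatological events: two SMQs.
- Renal events: two HLTs, one of them "Renal failure and impairment (MedDRA HLT".

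Protocol 8.2.1 describes the local reaction this way: "Symptoms of a local infusion site reaction may include erythema, induration, pain, pruritus, and edema". On collection it says: "If an infusion site event is reported, the AE will be recorded, and additional data will be provided to the sponsor in the CRF".

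SAP 6.17 names "Moderate to severe infusion site reactions" as a key safety event in the hypersensitivity domain and gives no term list. SAP 8 plans treatment-emergent events by preferred term, by preferred term within system organ class and by maximum severity, with listings.

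**The concern.** Infusion site reactions are the only AESI group in SAP 6.12.3 with no SMQ or HLT behind them. The systemic infusion-related term is also a single preferred term, but it sits beside four SMQs that can pick up related events. The local group has no such support.

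The protocol collects at a wider level: any infusion site event, described by its signs, triggers extra CRF data. If an investigator reports a sign at the infusion site and it is coded to a term for that sign, the event is collected as an infusion site event but is not retrieved by a search on one general term.

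At stake is the participant-level count of local reactions, which an AESI summary exists to give. The same count may be wanted for the SAP 6.17 key event, which has no search of its own in the supplied documents.

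**Working it through.** The documents give no expected rate of infusion site reactions and no coding split, so there is no planned figure to reproduce. The check compares the texts and then shows how an undercount would scale.

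**1. Search level by AESI group (SAP 6.12.3)**

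| Group | Grouped search | Single preferred term |
|---|---|---|
| Infusion site reactions | none | the label itself, no terms named |
| Hypersensitivity and infusion-related | 4 SMQs | 1 |
| Dermatological | 2 SMQs | none |
| Renal | 2 HLTs | none |

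**2. Two readings of the label**
- *One term.* The same tag is attached to the infusion-related reaction entry, where it marks a single term. Applied in the same way here, a reaction coded to any other term is not retrieved.
- *Several terms.* The entry is plural and the AESIs are displayed by preferred term, so a set may be meant. The set is not stated, so two programmers could produce different counts.

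Both readings call for the same edit.

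**3. Can the SAP 8 tables supply the count?** Not by themselves. Suppose two sign-level rows each show 5 participants. If the same 5 people had both signs, 5 participants had a local reaction. If they were different people, it was 5 + 5 = 10. The rows are identical in both cases. The count could be rebuilt from the listings, but no planned row shown in the documents gives it.

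**4. Illustration of size**

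Input from the documents: 100 participants on LY3016859 (Protocol 1.1). Assumptions that are not in the documents: p, the true incidence of any local reaction; f, the share of affected participants whose event carries the general term; participants independent.

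Expected number captured = 100 × p × f. Chance of capturing at least one = 1 − (1 − p × f)^100.

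| p | f | Affected | Captured | Chance of at least one |
|---|---|---|---|---|
| 5% | 100% | 5 | 5 | 0.994 |
| 5% | 80% | 5 | 4 | 0.983 |
| 5% | 50% | 5 | 2.5 | 0.920 |
| 5% | 20% | 5 | 1 | 0.634 |
| 10% | 100% | 10 | 10 | 1.000 |
| 10% | 80% | 10 | 8 | 1.000 |
| 10% | 50% | 10 | 5 | 0.994 |
| 10% | 20% | 10 | 2 | 0.867 |

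**5. Effect on the comparison between arms.** Assume 10% on LY3016859, 4% on placebo and the same f in both arms. The true difference is 10 − 4 = 6 points.
- f = 50%: 5.0% against 2.0%, a difference of 3.0 points.
- f = 20%: 2.0% against 0.8%, a difference of 1.2 points.

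The ratio is 2.5 in every case. The absolute difference shrinks by the factor f; the ratio does not.

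**The case against.** The strongest reply is that the narrow search is a reading, not the text. The entry is plural and names no term, and the lead-in says only that AESIs are shown by preferred term. This stands: the wording is ambiguous. It does not dispose of the point, because the other reading leaves the set of terms open.

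A reader might infer that the SAP contradicts a protocol definition. It does not. The protocol's list of signs is illustrative, and its own AESI section (8.2.3) covers only dermatological reactions and renal function. The mismatch is with what the protocol collects.

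A reader might also infer that most local reactions would be missed. That requires f below 50%, and the documents give no value for f. Whether each sign is coded to its own term depends on MedDRA and the sponsor's coding conventions, which neither document sets out. An investigator could equally report the diagnosis of infusion site reaction, and that would be retrieved.

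Nor would events vanish from safety reporting. They must be recorded as adverse events and would appear in the general tables and listings of SAP 8. This limits the harm to the AESI summary.

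The link to SAP 6.17 is inferred. That section carries no preferred-term restriction and refers to the CPMP SAP Version 5 for the totality-of-evidence analysis.

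Finally, the CPMP SAP Version 5 was not available, and text after the AESI list is redacted, so a fuller search may exist. However, SAP 6.12 places the additional ISA-specific safety considerations in its own sections, and the entry itself is legible, so it should be able to stand without another document.

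**Conclusion.** The point holds in a limited form. SAP 6.12.3 states a search level for infusion site reactions that is narrower than the protocol's collection of those events, and it is the only AESI group without a grouped search. Followed literally, the AESI summary would leave out any local reaction coded to a sign-level term, and no planned output shown gives the number of participants with any local reaction.

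This rests on two conditions: that the label is applied as one preferred term, and that at least some reactions are coded by sign. The size is unknown. The illustration runs from no undercount (f = 100%) to 4 of 5 affected participants left out (p = 5%, f = 20%), and every p and f in it is assumed.

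The documents do not support a claim that most reactions are lost, that safety data go unreported, or that the SAP 6.17 count is necessarily affected. This is more than a missing detail, because the level that is stated can be programmed as written and give a low count. It is still a small correction.

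**What to change.** In SAP 6.12.3, replace the preferred-term label with a grouped search. Use either the MedDRA HLT for infusion site reactions (to be confirmed in the dictionary version in use) or a named list of infusion-site preferred terms fixed before unblinding. Add any event for which infusion-site CRF data were supplied under Protocol 8.2.1.

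Report by arm the number and percentage of participants with at least one such event, and keep the by-preferred-term display beneath it. State in SAP 6.17 that its infusion-site event uses the same set, restricted to moderate or severe events.

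An HLT has the advantage that its content is set by the dictionary and cannot be shaped by the terms seen in the data.

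The cost is a short SAP edit and a changed search filter, with no new data collection. The one downside is that reported local-reaction counts may rise, so they may not be directly comparable with any summary already produced under the present label.

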2.3.1. Risk Assessment

Potential Risk of Clinical Significance	Summary of Data/Rationale for Risk	Mitigation Strategy
Study Intervention LY3016859		
Development TE ADA.	Incidence of TE ADA was 50% after a single dose, and up to 57% after multiple doses.	Collect samples up to 20 weeks after last dose to characterize ADA profile.
IV infusion may be associated with infusion reactions and hypersensitivity reactions.	LY3016859 is a monoclonal antibody that will be administered via IV infusion. Hypersensitivity reactions and infusion reactions may occur during treatment with such agents.	Monitor infusion reactions and hypersensitivity reactions. Guidance on management of infusion and hypersensitivity reactions are in Sections 8.2.1 and 8.2.2.
Dermatological adverse reactions similar to EGFR antagonists.	One healthy participant who received a single dose of 1 mg LY3016859 experienced a rash that was considered similar to those associated with EGFR antagonists.	Collect dermatological AEs. Stop dosing for severe dermatological AEs.
Changes in eGFR in participants with CLBP.	A modest and non-statistically significant decrease in eGFR was observed in participants with DN who received LY3016859 in Part B of Study TGAB, but not in healthy participants in Study TGAA.	Exclude participants with moderate or severe renal impairment in the study. Short dosing duration. Monitor eGFR and stop dosing if necessary. CCI [REDACTED]
Fetal harm due to in utero exposure	No effects on embryo-fetal development in enhanced pilot embryo-fetal development studies in rats and rabbits. Definitive developmental and reproductive toxicity studies are not yet completed.	Do not enroll women who are pregnant or breastfeeding in studies for LY3016859.
Study Procedures		
Participant may experience increased CLBP symptoms.	Medications that relieve CLBP pain will not be allowed until Visit 801.	Rescue medication is permitted. Standard treatment of CLBP may be restarted after Visit 801 based on investigator discretion.

Abbreviations: ADA = anti-drug antibodies; AE = adverse event; CLBP = chronic low back pain; DN = diabetic nephropathy; EGFR = epidermal growth factor receptor; eGFR = estimated glomerular filtration rate; IV = intravenous; TE = treatment emergent; TGAA = Study I5V-MC-TGAA; TGAB = Study I5V-MC-TGAB.

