7.1. Discontinuation of Study Intervention

If the investigator, after consultation with the sponsor-designated medical monitor, determines that a systemic hypersensitivity reaction or a serious infusion reaction has occurred related to study intervention administration, the participant should be permanently discontinued from the study intervention.

A participant should be discontinued from study intervention if they experience a dermatological adverse reaction, such as acneiform rash, that is related to study intervention, and is either mild to moderate and does not respond to topical treatment or is severe. The participant may continue in the study at the discretion of the investigator in consultation with the medical monitor or study sponsor physician/scientist.

8. Study Assessments and Procedures

Study procedures and their timing are summarized in the CPMP Master Protocol, CLBP CPMP(2) DSA, and ISA BP01 SoAs.

LY3016859-specific assessments and procedures are described here.

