8.2.3. Adverse Events of Special Interest

Dermatological adverse reactions

EGFR antibodies or EGFR-associated TKI are associated with various dermatological AEs, including acneiform rashes, xerosis, pruritis, and photosensitivity. Secondary infection can also develop.

Participants should use sun protection during the study period. Dermatological adverse reactions should be managed by the investigator according to standard of care. Discontinuation of treatment may be considered if these AEs do not respond to topical treatment, are widespread (>30% body surface area), or are severe.

If any of these AEs are reported, sites will be prompted to provide additional information.

Renal Function

Changes in eGFR were observed in participants with DN in Study TGAB (Section 2.2). Such changes were reversible and were not associated with an increase in proteinuria. Blood and urine samples will be collected to characterize the effects of LY3016859 on renal function, and eGFR will be monitored during the study.

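### The visible dermatological AESI search in SAP 6.12.3 names only two severe-reaction SMQs, so the separate AESI report may not show the EGFR-type skin reactions that protocol 8.2.3 flags

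*SAP*

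**What the plan says.** **Protocol.** Section 8.2.3 has a heading for dermatological adverse reactions among the AESIs. It states: "EGFR antibodies or EGFR-associated TKI are associated with various dermatological AEs, including acneiform rashes, xerosis, pruritis, and photosensitivity". It adds: "Secondary infection can also develop". On data collection it says: "If any of these AEs are reported, sites will be prompted to provide additional information". It gives no severity threshold for reporting. The risk table in section 2.3.1 bases the concern on one healthy participant given a single 1 mg dose, who "experienced a rash that was considered similar to those associated with EGFR antagonists". Section 7.1 covers a dermatological reaction "such as acneiform rash, that is related to study intervention, and is either mild to moderate and does not respond to topical treatment", as well as a severe one.

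**SAP.** Section 6.12.3 sets the reporting rule: "Treatment emergent adverse events of special interest will be reported separately by preferred term". Under dermatological adverse events it lists two searches:
- "Severe cutaneous adverse reactions (SMQ")
- "Drug reaction with eosinophilia and systemic symptoms syndrome (SMQ")

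Section 6.17 has one dermatological item, limited to serious or severe reactions. It also counts treatment discontinuation due to an adverse event, without a severity limit. Section 8 repeats the ISA-specific AESI report for the double-blind and follow-up periods combined and names no further search.

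**The concern.** The protocol picks out a skin-reaction profile expected from the drug's mechanism, asks sites for extra detail when such reactions occur, and cites an observed event of that type. The SAP's dermatological searches are, by their titles, aimed at something else: severe cutaneous syndromes and DRESS. A separate AESI table exists so that a reader can see the flagged risk in one place. Programmed as written, the dermatological part of that table could be nearly empty even if acneiform rash, dry skin, itching or photosensitivity were more common on LY3016859. The reader would then have to find those events in the general tables and choose the terms to group, possibly after seeing the data by arm.

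**Working it through.** The plan gives no figure to reproduce on this point. The check sets the texts side by side.

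**1. Reactions against searches.** Each reaction in protocol 8.2.3 is compared with the titles of the two dermatological searches in SAP 6.12.3.

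| Reaction in protocol 8.2.3 | Named in the severe cutaneous SMQ title? | Named in the DRESS SMQ title? |
|---|---|---|
| Acneiform rash | No | No |
| Xerosis | No | No |
| Pruritus | No | No |
| Photosensitivity | No | No |
| Secondary infection | No | No |

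None of the four named reaction types, and none of the five if secondary infection is included, is named. The visible bullet also gives no preferred term, high-level term or custom list for any of them. This count compares titles only. It does not show which terms the SMQs contain.

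**2. Severity.** Protocol 8.2.3 attaches no severity condition to its prompt for additional information. Protocol 7.1 includes mild to moderate reactions, on two conditions: they are related to study intervention and do not respond to topical treatment. Both SAP dermatological searches are for severe syndromes by name, and the dermatological item in 6.17 is limited to serious or severe events.

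**3. Other routes by which the events could be seen.**
- General tables: section 8 plans treatment-emergent and post-treatment-emergent events by preferred term, by preferred term within system organ class, and by maximum severity, with listings.
- The Hypersensitivity SMQ in 6.12.3 may catch some rash or itching terms, but under a different AESI heading.
- Treatment discontinuations due to adverse events are counted in 6.17 at any severity.

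None of these is a dermatological search directed at the reactions in protocol 8.2.3.

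**4. Illustration of the grouped count only.** This does not measure the defect. It shows why the fix includes a count of participants with any listed event. Assumptions: 100 LY3016859 and 50 placebo participants; four mutually exclusive terms; placebo total 4%; Fisher exact two-sided p < 0.05 with LY3016859 higher, used only as a yardstick because these documents plan no test of adverse events. The grouped row is the sum of binomial(100, p) × binomial(50, 0.04) probabilities over the tables that meet this criterion. The other rows come from 200,000 simulated trials per scenario and give the chance that at least one single term meets it.

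| Comparison | LY total 12% | LY total 16% | LY total 20% |
|---|---|---|---|
| Grouped | 27.5% | 57.1% | 80.7% |
| Any single term, equal split | 0.8% | 4.6% | 15% |
| Any single term, 55/15/15/15 | 7.5% | 21% | 39% |
| Any single term, 70/10/10/10 | 14% | 33% | 56% |
| Any single term, 85/5/5/5 | 21% | 45% | 70% |

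The gain from grouping shrinks as one term dominates. All rates and splits are assumed.

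**The case against.** The strongest reply is that little is at stake. The AESI list is introduced with inclusive wording, so it is not formally exhaustive. The protocol's examples describe EGFR inhibitors as a class; they neither define this trial's AESI search nor prescribe a table. SAP 6.12.3 reports AESIs by preferred term, so a longer list in that format would largely repeat rows already planned in the general tables. Some of the events may be picked up by the Hypersensitivity SMQ. The general adverse event analysis is deferred to the master SAP (CPMP SAP Version 5), which was not available. Redacted blocks follow the list; they probably belong to sections 6.12.4 and 6.12.5, but a redacted addition to 6.12.3 cannot be wholly excluded.

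All of this stands as a limit on the consequence. It does not remove the mismatch. SAP 6.12 says that ISA-specific safety considerations are given in its own subsections, and the only dermatological searches visible there are the two SMQs. Leaving the list open defers the choice of mechanism-related terms. An event caught under hypersensitivity is reported as a different risk, although protocol 2.3.1 lists the two risks separately. The point about repeated rows is why the fix includes a participant-level count.

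A reader might infer that the plan would hide or lose a skin signal, or that the two searches would capture none of these reactions. The documents support neither: the events remain in the general tables and listings, and a search title does not reveal its contents.

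**Conclusion.** The point holds as a mismatch between the protocol's description of the dermatological AESI and the visible search that implements it. Its size in events cannot be stated. From the text, none of the five reactions in protocol 8.2.3 is named in the two searches, and no visible dermatological entry in the SAP is directed at mild or moderate reactions of this type. That the AESI report may show few of them is a reasonable expectation from the search titles, but it depends on SMQ contents, the master SAP and redacted text that could not be checked. This is a cheap improvement with medium confidence. It does not bear on the primary analysis or on data collection.

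**What to change.** 1. In SAP 6.12.3, add a MedDRA term list for the dermatological AESI that matches protocol 8.2.3 at all severities: acneiform and other rash, dry skin, pruritus, photosensitivity and secondary skin infection.
2. Keep the severe cutaneous and DRESS SMQs as a severe subset.
3. Use the same definition for the AESI report in section 8.
4. Beyond the by-preferred-term format, report the number of participants with at least one listed event by arm and maximum severity.
5. Fix the list before the relevant unblinding. SAP Version 2 preceded unblinding for the PoC lock, and Version 3 was approved before the final lock. A list added after the PoC lock should be labelled as defined post hoc for PoC-lock data.

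If the master SAP or redacted text already contains such a list, a cross-reference in 6.12.3 is enough. No change to 6.17 is needed.

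**Cost.** SAP wording, one term list and one table, all from data already collected. Background rash and pruritus will be counted in both arms, which the placebo group helps to interpret. Some events may also count under the hypersensitivity AESI; a footnote should say so.
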